3.3.4.1 Discontinuation of the trial

Boehringer Ingelheim reserves the right to discontinue the trial overall or at a particular trial site at any time for the following reasons:

1. At least 2 subjects at one dose level within one population type, on active drug showed serum potassium levels ≥ 5.5 mmol/L in non-haemolysed blood
2. At least 2 subjects at one dose level within one population type, on active drug showed relevant individual QT prolongation, i.e. a QTcF increase of greater 60 ms from baseline (mean where applicable) in connection with absolute QT or QTcF greater than 500 ms, which has been confirmed by a repeat ECG recording. For CF subjects, the baseline for Treatment Period 2 will be calculated again at Visit 3 Day 1.
3. Failure to meet expected enrolment goals overall or at a particular trial site.
4. Emergence of any efficacy/safety information invalidating the earlier positive benefit risk- assessment that could significantly affect the continuation of the trial.
5. Violation of GCP, the CTP, or the contract disturbing the appropriate conduct of the trial.
6. New toxicological findings or serious adverse events invalidate the earlier positive benefit-risk-assessment.
7. For healthy volunteers, in the event of any subject having an, at least, possibly related SAE or in case of the occurrence of two, at least, possibly related severe AEs the study group will be halted. No further dosing, dose escalation or inclusion of any further subjects at the same dose will occur without approval of a substantial amendment
8. For CF subjects, in the event of 2 subjects having an, at least, possibly related SAE or in case of the occurrence of three, at least, possibly related severe AEs the study group

will be halted. No further dosing, dose escalation or inclusion of any further subjects at the same dose will occur without approval of a substantial amendment

The Investigator / the trial site will be reimbursed for reasonable expenses incurred in case of trial termination (except in case of the fifth reason).

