Fertility has not been assessed in nonclinical species, but no adverse effects have been observed on reproductive organs in 4-week toxicity studies in rats and dogs, suggesting that there is a low risk to fertility. At the time this current study is planned to start, embryo-fetal development studies of BI 443651 will not have been conducted. Therefore only female subjects of child bearing potential willing to accept highly effective methods of contraception [See exclusion criteria [section 3.3.3](#) for definition of highly effective methods of contraception] through the duration of this study and for 30 days after will be included, otherwise only males, and females of non-child bearing potential and non-lactating women will be included in this study.

The nonclinical safety studies (safety pharmacology and pivotal toxicity studies) to support the clinical study 1363.2 are described and referred to in the Investigator's Brochure for BI 443651 in Cystic Fibrosis and COPD. These studies have been conducted in compliance with Good Laboratory Practice and have been carried out in an OECD country.

The only exception is the study on the effects of BI 443651 on the hERG (human ether-a-go-go related gene)-mediated potassium current [[n00248843](#)]. This study was performed in an OECD country but without formal adherence to the principles of GLP (non-GLP). Data quality and integrity of the study however are given as study reconstruction is ensured through adequate documentation of the study conduct and archiving of data. Therefore the validity of the study is considered not compromised by its non-GLP status and as such there is no impact on the evaluation of the respective endpoints of this safety pharmacology study.

Whilst not all safety effects may be predicted, based on mechanism and systemic toxicological finding the only potential systemic toxicity is changes in serum electrolytes and particularly increases in serum potassium. These changes are easily monitored and treatable if observed. The following safety measures will be applied in this study in order to minimize the risk for the healthy volunteers and CF subjects:

- Frequent safety laboratory testing will be performed with a focus on electrolytes (see [Flow Chart I](#) & [Flow Chart II](#)). Dose escalation will be stopped as soon as at least 2 subjects at one dose level within one population type on active drug showed serum potassium levels ≥ 5.5 mmol/L in non-haemolysed blood

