3. DESCRIPTION OF DESIGN AND TRIAL POPULATION

3.1 OVERALL TRIAL DESIGN AND PLAN

This trial will be composed of two parts – a multiple rising-dose (MRD) part and a cross-over part. Both parts will be randomised, placebo-controlled and double-blind.

Part 1 (MRD): MRD part will be double-blind within dose groups and includes healthy volunteers.

A total of 40 healthy volunteers are planned to participate in the trial according to 4 sequential dose groups compromising 10 subjects per group. Within each dose group 8 volunteers will receive the active drug and 2 will receive placebo.

For healthy volunteers, one dose will be tested within each dose group. The groups will be treated consecutively in ascending order of dose. The dose groups to be evaluated are as outlined in Table 3.1: 1 below.

Additional subjects may be entered to allow testing of additional (e.g. intermediate) doses within the planned dose range on the basis of experience gained during trial conduct, i.e. the actual number of subjects entered in Part 1 may exceed 40 subjects. Such a change would be implemented as a non-substantial CTP amendment provided that the additional dose levels to be tested were within the approved dose range.

Table 3.1: 1 Dose groups for Part 1 (MRD) and Part 2 (cross-over)

| Dose group | 1 | 2 | 3 | 5 | 7 |
|------------------------------------|------------------|------------------|-------------------|-------------------|------------------|
| Subjects | HV | HV | HV | HV | CF |
| Dose | 100 µg b.i.d. | 400 µg b.i.d. | 1200 µg b.i.d. | 1800 µg b.i.d. | 600 µg b.i.d. |
| Daily dose (µg) | 200 | 800 | 2400 | 3600 | 1200 |
| No. of subjects | 10 | 10 | 10 | 10 | 24 |
| Subjects on placebo | 2 | 2 | 2 | 2 | 24 |
| Subjects on active drug | 8 | 8 | 8 | 8 | 24 |

For healthy volunteers four different dose groups (100, 400, 1200 and 1800 µg b.i.d.) will be investigated consecutively in ascending order of daily doses (see [section 3.1.2](#) for information on dose escalation).

Part 2 (cross-over): 24 CF subjects will be included in the second part of the study (cross-over design). Each CF subject will receive both placebo and the active drug at one dose-level in a randomised sequence with 12 subjects on each of the following sequences: Active/Placebo, Placebo/Active (See [section 3.1.1](#) for starting rules).

3.1.1 Start of CF dose groups:

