The second part of the study including CF subjects will only start once the 1200 µg b.i.d dose been shown to be well tolerated in healthy volunteers ([see table 3.1.2: 1](#)).

The decision to administer BI 443651 to CF subjects will be taken in a documented safety review meeting ([see section 3.1.2](#)).

3.1.2 Dose escalation:

The dose groups will be investigated consecutively in ascending order of doses with a dose escalation review between each dose group.

Healthy volunteers: The healthy volunteer dose groups will be investigated first. Each cohort of healthy volunteers, 10 subjects (8 on active, 2 on placebo) will be dosed up to 7 days in an incremental order with a dose escalation meeting in between each dose step. Only if the previous dose of BI 443651 is safe and well tolerated in the prior dose group, without meeting any stopping criteria (see [Section 3.3.4.1](#)), will the subsequent dose be administered ([see table 3.1.2: 1](#)).

For each dose level in healthy volunteers, the dosing of the first subject in subsequent dose groups will be separated by at least 9 days, implying at least 7 days of blinded safety and tolerability data from the preceding dose group, which is expected to cover the period to predicted steady state.

Table 3.1.2: 1

Dose escalation schedule (b.i.d.)

| Time | Healthy volunteer | CF |
|---|-------------------|--------------|
|  | DG1 (100 µg) | - |
| | DG2 (400 µg) | - |
| | DG3 (1200 µg) | - |
| | DG5 (1800 µg) | DG7 (600 µg) |
| | - | - |

A documented dose escalation safety review meeting must take place prior to each dose escalation. Furthermore, an unscheduled safety review meeting can be requested anytime for any reasonable cause by the Principal Investigator (or an authorised deputy) or the sponsor of the study, e.g. because of any unforeseen adverse events, etc. Dose escalation will only be permitted if no safety concerns exist in the opinion of the safety review committee, with appropriate representation from Sponsor company and the Principal Investigator (or an authorised deputy).

The minimum data set for review consists of the following data on 8 Healthy Volunteers (see [section 3.3.5](#) for subject replacement):

- AEs in the current and preceding dose groups up to at least end of treatment (including clinically relevant findings from ancillary safety testing listed below) (Note: AEs may be ongoing at the time of Safety Reviews)
- Clinical laboratory tests in the current and preceding dose groups

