3.3.4 Removal of subjects from therapy or assessments

An excessive withdrawal rate can have a severe negative impact on the scientific value of the trial. Every effort should be made to keep subjects in the trial as scheduled. This includes careful subject selection and appropriate explanation of the trial requirements and procedures prior to enrolment as well as an explanation of the consequences of premature withdrawal.

An individual subject is to be withdrawn from trial treatment if:

- The subject has a confirmed increase in serum potassium of ≥ 5.5 mmol/L in non-haemolysed blood.
- The subject shows relevant individual QT prolongation, i.e. a QTcF increase of greater 60 ms (mean where triplicate is performed) from baseline (pre-dose Day 1) in connection with absolute QT or QTcF greater than 500 ms, which has been confirmed by a repeat ECG recording.
- CF: A CF exacerbation occurs during treatment (for definition see [Appendix 10.6](#)). Patients may continue in the study if an exacerbation occurs during the washout period between treatment period 1 and 2, provided that patients have been off antibiotics (IV or oral, prescribed for the exacerbation) for at least 4 weeks and FEV₁ has returned to within 10% of the baseline values. Treatment washout between the two treatment periods can be extended up to a maximum of 6 weeks.
- The subject withdraws consent for trial treatment or trial participation, without the need to justify the decision.

The investigator should ask the subject who withdraws consent whether the withdrawal is related to the further administration of trial medication or to all trial-related observations and procedures. The investigator should explain the importance of the further measures for the assessment of the subject's safety. The observations and procedures to be followed for subjects who terminate the administration of trial medication prematurely (please see details below) will be performed accordingly.

- The subject needs to take concomitant drugs that interfere with the investigational product or other trial medication ([see Section 4.2.2](#))

Proprietary confidential information © 2017 Boehringer Ingelheim International GmbH or one or more of its affiliated companies

- The subject experiences a serious adverse event or any AE, that in the opinion of the investigator, may jeopardise the safety of the trial participant.

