- The subject has repeatedly shown to be non-compliant with important trial procedures and, in the opinion of both, the investigator and sponsor representative, is not willing or able to stick to the trial requirements in the future.
- The subject can no longer be treated with trial medication for any medical reason (e.g. surgery, adverse events, other diseases, or pregnancy)
- Decision by Boehringer Ingelheim to discontinue treatment of a specific subject (for instance, in case of the occurrence of an SAE that would be incompatible with trial continuation)

Given the subject's agreement, the subject will undergo the procedures for early treatment discontinuation and follow up as outlined in [Flow Chart I](#) & [Flow Chart II](#) and [section 6.2.3](#).

For all subjects the reason for withdrawal (e.g. adverse events) must be recorded in the CRF. These data will be included in the trial database and reported. In case of patient's discontinuation, the investigator/site staff will inform the sponsor in a timely manner. This communication should always include the reason for withdrawal.

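### Part 2 has no mandatory group-level response to raised potassium: section 2.3.2 stops only dose escalation, and section 3.3.4.1 item 1 only reserves a right

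*Protocol*

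**What the plan says.** Protocol section 2.3.2 states that "the only potential systemic toxicity is changes in serum electrolytes and particularly increases in serum potassium". It then introduces a list with "The following safety measures will be applied in this study in order to minimize the risk for the healthy volunteers and CF subjects". The potassium entry in that list begins "Dose escalation will be stopped as soon as at least 2 subjects at one dose level within one population type on active drug" and sets the threshold at 5.5 mmol/L or above in non-haemolysed blood.

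Section 3.3.4.1 item 1 repeats the same trigger. Its lead-in reads "Boehringer Ingelheim reserves the right to discontinue the trial overall or at a particular trial site at any time for the following reasons", and the item adds no action.

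Section 3.1 describes Part 2 in these terms: "Each CF subject will receive both placebo and the active drug at one dose-level in a randomised sequence". That dose is 600 µg b.i.d., planned for 24 subjects.

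At the level of the individual, section 3.3.4 requires withdrawal from treatment under a criterion that begins "The subject has a confirmed increase in serum potassium of" and uses the same 5.5 mmol/L threshold. When a patient discontinues, "the investigator/site staff will inform the sponsor in a timely manner", with the reason. Under section 3.1.2, "an unscheduled safety review meeting can be requested anytime for any reasonable cause by the Principal Investigator" or by the sponsor.

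**The concern.** The potassium rule is presented as protecting both populations, but its one mandatory action has no effect in the second. In Part 1 the rule binds: section 3.1.2 allows the next healthy-volunteer dose only if no stopping criterion has been met. Part 2 has no next dose, so nothing turns the criterion into an obligation.

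After a second confirmed case on active drug, the sponsor would know of both withdrawals. The remaining CF subjects could nevertheless continue dosing with no required pause and no required review. These subjects are spread over at least six sites and dose at home on most days, so one investigator may see only one of the two cases. The group-level decision should therefore not depend on someone choosing to ask for a meeting.

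**Working it through.** **Step 1. Compare the group-level rules as they apply to CF subjects.**

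| Rule | Trigger | Action stated | Effect in Part 2 |
|---|---|---|---|
| Potassium, 2.3.2 | 2 or more on active, K at or above 5.5 mmol/L | Escalation stops (mandatory) | None: one dose level |
| Potassium, 3.3.4.1 item 1 | Same | None in the item; lead-in reserves a right | Optional |
| QT, 2.3.2 | 2 or more on active, confirmed prolongation | Dosing stops (mandatory) | Binding |
| SAE or severe AE, 3.3.4.1 item 8 | 2 subjects with possibly related SAEs, or 3 possibly related severe AEs | Group halted; no dosing without a substantial amendment | Binding, but depends on AE classification |

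The protocol states mandatory CF actions for QT, where it reports no preclinical signal, and for serious or severe events. For potassium, the risk it expects, it does not.

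**Step 2. Look for another mandatory route.** Sections 3.1.1, 3.1.2, 3.3.4, 4.1.2, 4.1.5.2, 5.3.7 and 7.4 supply none. Individual withdrawal is mandatory but acts on one subject. The unscheduled review, the investigator's power to stop dosing (4.1.2) and the other 3.3.4.1 grounds for stopping on benefit-risk are discretionary.

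**Step 3. Check the wording of the threshold.** Section 3.3.4 requires a confirmed value. The group rules in 2.3.2 and 3.3.4.1 item 1 do not.

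**Step 4. How often would the trigger be met?** The documents state no figure for this rule, so there is none to reproduce. Inputs: n = 24 CF subjects, all planned to receive active drug (3.1); n = 8 active subjects in one healthy-volunteer dose group (3.1); n = 20, the minimum number of CF completers (3.3.5). The per-subject rate p of a confirmed value is assumed, with independent subjects:

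P(at least 2) = 1 − (1 − p)^n − n·p·(1 − p)^(n−1)

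At p = 0.05 and n = 24: 1 − 0.95^24 − 24 × 0.05 × 0.95^23 = 1 − 0.2920 − 0.3688 = 0.339.

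At p = 0.05 and n = 8: 1 − 0.95^8 − 8 × 0.05 × 0.95^7 = 1 − 0.66342 − 0.27933 = 0.05725, or 0.057.

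| Assumed p | One HV group, n = 8 | CF, n = 20 | CF, n = 24 |
|---|---|---|---|
| 1% | 0.003 | 0.017 | 0.024 |
| 2% | 0.010 | 0.060 | 0.083 |
| 5% | 0.057 | 0.264 | 0.339 |
| 10% | 0.187 | 0.608 | 0.708 |

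The same count of two is reached more easily in the larger Part 2 group. That bears on the choice of response: a pause for review on confirmed values is proportionate, whereas automatic termination would not be.

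**The case against.** The strongest reply is that nothing essential is missing. The lead-in to 3.3.4.1 does name a consequence, discontinuation of the trial or a site, which is stronger than a pause, and the item reaches CF subjects. Whether such a criterion is automatic or judged is a matter of preference. Several protections also apply:

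- Every subject with a confirmed value is already off drug.
- Local potassium results govern dosing decisions (5.3.7).
- Subjects with potassium above the normal range or with chronic kidney disease are excluded, and potassium-altering drugs are barred.
- CF dosing starts only after 1200 µg b.i.d. has been tolerated and a documented review held.
- Hyperkalaemia reported as serious or severe could trigger item 8.

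This limits the risk but does not fill the gap. These measures act on individuals, apply before dosing starts, are discretionary, or depend on how an event is classified. Two subjects without symptoms at 5.5 mmol/L need not meet item 8.

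A second reply is that comparing 24 with 8 exaggerates the contrast, because Part 1 has four active groups. At p = 0.05 the chance that at least one group triggers is 1 − (1 − 0.05725)^4 = 0.210, so the ratio is 0.339/0.210 = 1.6, not 0.339/0.057 = 5.9. The arithmetic is right, but the rule counts per dose level, so 8 is its unit. The case for a mandatory response does not rest on either ratio.

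A third reply stands in part. The trigger counts subjects on active drug while the trial team is blinded, so applying it means breaking the code for each case. That belongs in the cost of the change.

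**Conclusion.** The concern holds. In Part 2 the stated potassium safeguard requires no action beyond the affected individual, and no other section supplies one. Detection and authority are in place: withdrawal is mandatory, sites report the reason, a review can be requested, and the clause in 4.1.5.2 on protecting subjects' safety can support a code break. What is missing is an obligation at group level.

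The prior risk is limited. Section 2.3.2 reports no relevant electrolyte effects up to 1800 µg b.i.d., which is 1800/600 = 3 times the CF dose. That reassurance covers 6.5 days of dosing against 13.5 in CF, and SAP section 4 says it was unclear whether steady state had been reached by Day 7. The point concerns subject safety and changes no endpoint or analysis. The trigger probabilities of 0.024 to 0.708 rest wholly on assumed rates of 1% to 10% and independence; they describe how often a review would be called, not harm. The change should be made.

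**What to change.** In 2.3.2 and in 3.3.4.1 item 1, state that once two or more CF subjects on active drug have a confirmed serum potassium of 5.5 mmol/L or above in non-haemolysed blood, further Part 2 dosing is paused until a documented safety review has taken place. In 4.1.5.2, extend the stopping-criteria clause, which now names only escalation decisions, to cover this one, and say who breaks the code for each case. The QT rule needs no change.

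The cost is an amendment, a code break for each qualifying case and possibly a temporary pause of Part 2. At an assumed 5% rate the pause would be called with probability 0.339. This is acceptable because only confirmed values count, the action is a review and not termination, and the subjects whose codes are broken have already been withdrawn from treatment.

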3.3.5 Subject replacement

If more than 2 healthy volunteers per dose group do not complete up to the end of the dosing periods, the trial clinical monitor together with the trial pharmacokineticist and the trial statistician are to decide if and how many subjects will be replaced.

A sufficient number of CF subjects (planned 24) should be recruited to ensure at least 20 completed both dosing periods. If less than 20 subjects complete both dosing periods, the trial clinical monitor together with the trial statistician are to decide if and how many subjects will be replaced.

To be considered as completing the dosing period, volunteers or subjects are required to be 80 - 120% compliant with treatment ([section 4.3](#)).

A replacement subject will be assigned a unique study subject number, and will be assigned to the same sequence as the subject he/she replaces.

4. TREATMENTS

4.1 INVESTIGATIONAL TREATMENTS

The study medication below will be supplied by Boehringer Ingelheim Pharma GmbH & Co. KG

1 mg BI 443651 (MW 571.12 g/mol) equals 1.26 mg BI 443651 salt form (MW 721 g/mol). The doses given below refer to the respective free base.

BI 443651 inhalation solution is administered via the Respimat® inhaler (Version 5).

4.1.1 Identity of the Investigational Medicinal Products

Table 4.1.1: 1 Test product:

| | |
|-----------------------------|------------------------------------|
| Substance: | BI 443651 |
| Pharmaceutical formulation: | inhalation solution |
| Source: | BI Pharma GmbH & Co. KG, Germany |
| Unit strength: | 100 µg/actuation, 300 µg/actuation |
| Posology | b.i.d. |
| Route of administration: | Inhalation |
| Device: | RESPIMAT A5 |
| Duration of use: | 6.5 days, 13.5 days |

Table 4.1.1: 2 Placebo:

| | |
|-----------------------------|----------------------------------|
| Substance: | Placebo to BI 443651 |
| Pharmaceutical formulation: | inhalation solution |
| Source: | BI Pharma GmbH & Co. KG, Germany |
| Unit strength: | Not applicable |
| Posology | b.i.d. |

Table 4.1.1: 2

Placebo (cont.):

| | |
|--------------------------|---------------------|
| Route of administration: | Inhalation |
| Device: | RESPIMAT A5 |
| Duration of use: | 6.5 days, 13.5 days |

A placebo matching the Respimat® platform Inhalation Solution will be used. It uses the same excipients as the verum. All Respimat® treatments will be double-blind.

4.1.2 Selection of doses in the trial

The dose levels to be studied in this trial are 100 µg, 400 µg, 1200 µg and 1800 µg b.i.d. in healthy volunteers and 600 µg b.i.d. in CF subjects. The background for this dose selection is described as follows:

Starting and maximum dose

Whilst 100 µg may be an efficacious dose, the selection of 100 µg as the starting dose is supported by the benign safety profile of BI 443651 observed in study 1363.1 at single doses of up to 3600 µg, including a lack of effect on serum electrolytes

To adequately address all these aspects 1800 µg b.i.d. has been selected as the maximum dose to be delivered in healthy volunteers. The highest doses for CF subjects will be 600 µg b.i.d. administered once the 1200 µg b.i.d. dose level is confirmed as safe and well tolerated in healthy volunteers.

The investigator can decide at any time to discontinue dosing, to decrease the dose escalation by adding intermediate doses in case of intolerability or decrease the dose based on safety concerns.

